Appendix 5. Protocol Amendment I7W-MC-UDAA(c) Summary

Protocol I7W-MC-UDAA has been amended; the new version is indicated as amendment (c) and will be used to conduct the study in place of any preceding version of the protocol.

The overall changes and rationale for the changes made to this protocol are as follows:

Section	Changes made	Rationale for the change
6.1 Inclusion Criteria	Removed time frame for admission to the hospital and increased SpO ₂ to 95%	Feedback from sites regarding baseline SpO ₂ in admitted patients; to allow including moderately ill patients
6.2 Exclusion Criteria	Exclusion criteria revised to 
 • remove ineligibility of patients with DNI orders • not exclude patients with active malignancies or patients with postorgan transplant • delete BMI criteria as long as proning is possible • remove ineligibility of patients anticipated to receive or receiving anticoagulants • clarify “active” vasculitis • replace “symptomatic” with “chronic” congestive heart failure and clarify wording 	Following evolving feedback from clinical sites and FDA to include patients who have the greatest need to be enrolled in the study.
7.1 Treatments Administered	Added a footnote to the table to reflect a maximum dose of 3000 mg	For consistency with existing instructions in the Pharmacy manual
7.7 Concomitant Therapy	Amended to include 
 • anticoagulation therapies at any time during the study • convalescent antibodies, and • remdesivir 	Following evolving feedback from clinical sites and FDA
8.1 Discontinuation from Study Treatment	Added discontinuation for bleeding events	Per FDA feedback
10.3.6 Interim Analysis	Added the potential for a futility analysis	Per FDA feedback

Revised Protocol Sections

Note: Deletions have been identified by ~~strike-throughs~~ or grayed out for figures. Additions have been identified by the use of underscore.

6. Study Population

6.1 Inclusion Criteria

Patients are eligible to be included in the study only if they meet all of the following criteria at screening, unless specified otherwise:

1. Must be admitted to the hospital ~~for less than 48 hours~~
2. Confirmed pneumonia with:
 - a. Presence of signs and symptoms of respiratory disease (ie, cough, tachypnea, and/or shortness of breath)
 - and at least one of the following**
 - b. Infiltrates on chest imaging
3. oxygen saturation (SpO₂) of ~~≤95%~~≤93% on room air

6.2. Exclusion Criteria

Patients will be excluded from study enrollment if they meet any of the following criteria at screening, until specified otherwise:

1. Have ARDS and/or require immediate intermittent mandatory ventilation (IMV) ~~or are ineligible for IMV due to a pre-existing medical condition, including those with DNI orders.~~
3. Any concurrent serious medical condition (e.g. ~~active malignancies on chemotherapy, post organ transplant,~~ patients with estimated glomerular filtration rate [eGFR] <15 mL/min/1.73m² or on dialysis, preexisting lung disease requiring O₂ at rest, body mass index [BMI] ≥40 kg/m² that precludes techniques such as proning) or concomitant medication that in the opinion of the investigator that would preclude participation in the study.
7. Exclusion Criterion [7] has been deleted. ~~At the time of study drug administration, anticipated to be requiring full-dose (therapeutic) anticoagulation with warfarin and/or other anticoagulants~~

~~Patients receiving prophylactic, low-dose anticoagulation therapy are eligible provided that they are on low-molecular-weight heparin or oral Factor Xa inhibitors or it is medically appropriate at the investigator's judgment that patients switch to low-molecular-weight heparin or oral Factor Xa inhibitors before initiation of study therapy~~

8. Have a significant bleeding disorder or active vasculitis or had a Grade ≥ 3 bleeding episode within 12 weeks prior to receiving treatment
11. Have ~~chronic~~symptomatic congestive heart failure (New York Heart Association class ≥ 3) or ~~symptomatic or poorly~~ uncontrolled cardiac dysarrhythmia

7.1. Treatments Administered

Table 7-1. Treatment Regimens

Regimen	Dose Day 1	Dose Day 15
LY3127804	20 mg/kg	20 mg/kg
Placebo	Matching placebo	Matching placebo

Note: Patients weighing 150 kg and above will receive a maximum LY3127804 dose of 3000 mg. Please see the Pharmacy Manual for further instructions.

7.7. Concomitant Therapy

All concomitant therapies that are part of routine care are allowed and can be used during the study. If indicated, ~~after completion of study drug administration,~~ anticoagulation therapies, including full-dose anticoagulation therapies, are allowed.

All concomitant therapies must be recorded in the eCRF.

Concomitant medications captured should include unapproved (“off-label”) medication, such as, for example, convalescent antibodies, remdesivir, chloroquine, hydroxychloroquine, and IL-6 antagonists.

8.1. Discontinuation from Study Treatment

Possible reasons leading to permanent discontinuation of study drug:

- Patient Decision
 - the patient requests to discontinue study drug.
- Investigator Decision
 - The investigator may discontinue treatment after the first dose, if in the judgement of the investigator the benefit/risk assessment for LY3127804 does not support administration of a second dose.
- Grade 3 or higher infusion-related reaction per National Cancer Institute Common Terminology Criteria for Adverse Events (NCI-CTCAE) 5.0 (refer to Section 9.2.2).

- Grade 2 and greater bleeding events associated with study treatment.

10.3.6. Interim Analysis

An interim analysis may be conducted to assess efficacy results. The interim efficacy results may be used for internal decision-making to trigger planning activities associated with the investigational product and/or to assess futility. No adjustment of Type I error will be performed as the study will not be stopped for efficacy, and no modification of Study UDAA is expected~~will be~~ based on these interim results, other than possibly stopping the study for futility. The assessment would be conducted by a sponsor assessment committee with a limited number of preidentified team members who do not have direct site contact or data entry/validation responsibilities. Unblinding details will be specified in the unblinding plan section of the SAP or in a separate unblinding plan document. Information that may unblind the study during the analyses will not be reported to study sites or to the blinded study team until the study has been unblinded.

Document Approval Form

Document Information

Document Type	Protocol Amendment
Component ID	5cdb0673-4945-42f2-b8d0-18129ce3d83e
Document Title	UDAA 05 Protocol (c).pdf
Version Number	(c)
Storage Location	Leo Storage/Clinical/LY3127804/I7W-MC-UDAA/Clinical Protocol/LY3127804 I7W-MC-UDAA Clinical Protocol (c)/UDAA 05 Protocol (c).pdf

Compound and/or LY #	LY3127804
Study Identifier	N/A
Site Number	N/A
Investigator	N/A
Country	US

Comments

Complete this field to capture additional information.

Reviewer and Approver

REVIEWED BY: Only include the name(s) and the signature(s) of the individuals who are required to review the document by procedure. The signature(s) represents that the document and/or source has been reviewed for accuracy. Add or delete rows as necessary.

Name	Title	Signature	Date (dd-Mmm-yyyy)

APPROVED BY: Include the name(s) and signature(s) of the approver(s). The signature(s) represent(s) that the appropriate reviews have occurred and the document is appropriate for its intended use. THE LAST APPROVAL DATE IS USED AS THE APPROVAL DATE FOR THE DOCUMENT. Add or delete rows as necessary.

PPD

2.1 Primary Objective

The primary objective is to evaluate ventilator free days during treatment with LY3127804. This is defined as the number of days from Day 1 to Day 28 on which a patient breathes without assistance, if the period of unassisted breathing lasted at least 24 consecutive hours and the patient did not die within 28 days from first dose of study drug. If the patient died within 28 days, then this end point will be set equal to -1.

2.2 Secondary Objectives

Objectives	Endpoints

 To evaluate clinical status of patients during treatment with LY3127804 	
 NIAID ordinal assessment

 To evaluate survival without the need for IMV/ECMO 	
 Complete response is the proportion of patients who are alive and respiratory failure free (i.e. never having required mechanical ventilatory support) by Day 28

 To evaluate mortality rate during treatment with LY3127804 	
 Death within 28 days from first dose of study drug

 To evaluate reduction in hospital stay during treatment with LY3127804 	
 Length of hospitalization

 To evaluate safety of LY3127804 	
 AEs and SAEs

[figure not shown]
Abbreviations: AE = adverse event; NIAID = National Institute of Allergy and Infectious Diseases; SAE = serious adverse event; SpO₂ = oxygen saturation

3. Study Design

3.1 Summary of Study Design

Study I7W-MC-UDAA is a multicenter, randomized, double-blind, parallel, placebo-controlled Phase 2 study in patients who are hospitalized with a pneumonia and presumed or confirmed COVID-19.

Figure 1.0. Illustration of study design for Clinical Protocol I7W-MC-UDAA.

3.2 Determination of Sample Size

Approximately 210 patients may be enrolled in a 1:1 ratio to LY3127804 or placebo (105 per treatment group) in order that 200 patients complete the study. A sample size of 100 in each group will have 81% power to detect a difference between the placebo group and the LY3127804 group using a Wilcoxon rank-sum test with a 0.05 one-sided significance level. This powering is based on the following assumptions: intermittent mandatory ventilation (IMV) rate of 25% and mortality rate of 12.5% in the placebo group, 50% improvement in IMV rate and mortality rate for the LY3127804 group relative to placebo, and a mean difference (LY3127804 minus placebo) of 3.0 ventilator-free days where patients who die are assigned a value of -1.

3.3 Method of Assignment to Treatment

Patients who meet all criteria for enrollment will be stratified by age group (<65 years and ≥ 65 years), sex, and site, and then, on Day 1, randomly assigned in a 1:1 ratio within each stratum to receive either LY3127804 or placebo. Treatment assignment will be determined by a computer generated randomization sequence using an interactive web response system (IWRS).

4. A Priori Statistical Methods

4.1 General Considerations

Efficacy analyses will be conducted on the Efficacy Analysis Set; safety analyses will be conducted on the Safety Analysis Set. Analyses to be conducted on both the Efficacy set and the Safety set will not be replicated if the two Analysis sets are the same.

Descriptive statistics will include the number of subjects, mean, standard deviation, median, minimum, and maximum for continuous measures, and frequency counts and percentages for categorical measures. The minimum and maximum will be reported to the same number of decimal places as the raw data recorded in the database. The mean and median will be reported to one more decimal place than the raw data recorded in the database. The SD will be reported to two more decimal places than the raw data recorded in the database. Percentages will be presented to one decimal place. Percentages will not be presented for zero counts. Percentages will be calculated using n (the number of observations with non-missing values) as the denominator. In general, the maximum number of decimal places reported shall be four for any summary statistic.

Change from baseline will be calculated as the visit value of interest minus the baseline value. If all baseline values are missing for a particular variable, then the change from baseline and percent change (or percent improvement) from baseline will not be calculated.

All confidence intervals (CIs) and statistical tests will be two-sided unless otherwise specified. P-values which are greater than or equal to 0.001, and less than or equal to 0.999, will be presented to three decimal places. All other p-values which are less than 0.001 will be presented as '<0.001', while p-values greater than 0.999 will be presented as '>0.999'. CIs will be presented to one more decimal place than the raw data.

Unless otherwise noted, treatment comparisons of dichotomous variables will be made using Chi-square test. The proportions, difference in proportions, and 90% Wald confidence interval (CI) of the difference in proportions will be reported. Stratification is ignored in the analysis of dichotomous variables.

Unless otherwise noted, treatment comparisons of quantitative variables will be made using a restricted maximum likelihood-based mixed-effects model of repeated measures (MMRM). The model will include treatment, age group, sex, and site as fixed categorical effects, and, if applicable, study day as a continuous effect and treatment-by-study day interaction. The covariance structure to model the within-patient errors will be unstructured. If the available data cannot support the covariance structure (e.g., due to missing values), other structures will be attempted. If the unstructured covariance matrix results in a lack of convergence, the heterogeneous Toeplitz (TOEPH) covariance structure, followed by the heterogeneous autoregressive [ARH(1)] covariance structure, followed by the compound symmetry structure will be used. The first structure to yield convergence will be used for inference. The NewtonRaphson with ridging optimization technique will be used to aid with convergence. The Kenward-Roger approximation (KR2) will be used to estimate the denominator degrees of freedom and adjust standard errors. Type III tests based on the LS means will be used for the statistical comparison; the 90% CI will also be reported.

All tests of treatment effects will be conducted at a 1-sided alpha level of 0.05, unless otherwise stated. No adjustments for multiple comparisons will be made.

All computations for statistical analyses will be performed using SAS® software, Version 9.4 or later. All SAS programs used in the production of statistical summary outputs will be validated with independent programming prior to finalization. In addition, all program outputs will be independently reviewed. The validation process will be used to confirm that all data manipulations and calculations were accurately done. Upon completion of validation and quality review procedures, all documentation will be collected and filed by the project statisticians.

When implementing parametric methods of analysis, the distribution of analysis variables will be examined to determine if model assumptions are satisfied. Transformations or nonparametric methods of analysis may be added as sensitivity analyses if warranted. Whenever alternative methods of analysis are required, the description of the new method along with the rationale for its use will be documented in the Clinical Study Report (CSR).

Any change to the data analysis methods described in the protocol will require an amendment ONLY if it changes a principal feature of the protocol. Additional exploratory analyses of the data will be conducted as deemed appropriate.

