10.3. Statistical Analyses

10.3.1. General Statistical Considerations

Statistical analysis of this study will be the responsibility of Lilly or its designee. A detailed statistical analysis plan (SAP) describing the statistical methodologies will be developed.

Efficacy analyses will be conducted on the Efficacy Analysis Set; safety analyses will be conducted on the Safety Analysis Set.

Descriptive statistics will include the number of patients, mean, standard deviation, median, minimum, and maximum for continuous measures, and frequency counts and percentages for categorical measures.

Investigators with fewer than 2 randomized patients per treatment group will be pooled for statistical analysis purposes. Sensitivity analyses accounting for missing data will be described in the SAP.

Unless otherwise noted, treatment comparisons of discrete variables will be made using logistic regression analysis with treatment and randomization stratification variables in the model. The percentages, difference in percentages, and 95% confidence interval (CI) of the difference in percentages will be reported.

Unless otherwise noted, treatment comparisons of continuous variables will be made using a restricted maximum likelihood-based mixed-effects model of repeated measures (MMRM). The model will include treatment, age group, and site, and, if applicable, study day and treatment-by-study day interaction as fixed categorical effects. Additional details on the MMRM analyses will be described in the SAP.

All tests of treatment effects will be conducted at a 1-sided alpha level of 0.05, unless otherwise stated.

Any change to the data analysis methods described in the protocol will require an amendment ONLY if it changes a principal feature of the protocol. Any other change to the data analysis methods described in the protocol, and the justification for making the change, will be described in the clinical study report (CSR). Additional exploratory analyses of the data will be conducted as deemed appropriate.

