10.3.3.2. Secondary Analyses

Secondary end points will be described and compared between treatment groups. The NIAID ordinal scale and length of hospitalization will be analyzed with the Wilcoxon rank-sum test.

Mortality, survival without respiratory failure, and categorical changes on the NIAID ordinal scale will be analyzed as discrete variables.

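### SAP 4.1 drops the randomization strata from the Complete Response comparison, unlike Protocol 10.3.1; the likely cost is a little power, and 28-day mortality is hardly affected

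*SAP*

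**What the plan says.** SAP 3.3: "Patients who meet all criteria for enrollment will be stratified by age group", sex and site, and are then allocated 1:1 within each stratum.

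Protocol 10.3.1: "treatment comparisons of discrete variables will be made using logistic regression analysis with treatment and randomization stratification variables in the model", and the "95% confidence interval (CI) of the difference in percentages will be reported". Protocol 10.3.3.2 brings the two endpoints at issue under that rule: "Mortality, survival without respiratory failure, and categorical changes on the NIAID ordinal scale will be analyzed as discrete variables".

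SAP 4.1 replaces this with a chi-square test. It states that the "90% Wald confidence interval (CI) of the difference in proportions will be reported" and that "Stratification is ignored in the analysis of dichotomous variables". SAP 4.12.3.1 sends Complete Response to section 4.1 for its test and uses the strata only to tabulate rates. SAP 4.12.3.3 names no test for mortality, so the 4.1 default applies there too.

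Elsewhere the SAP keeps the strata: for the primary endpoint (4.12.1), worst NIAID score (4.12.3.2), length of stay (4.12.3.4) and the repeated-measures model (4.1). It ignores them for the log-rank test of time to 2-point improvement (4.12.3.2).

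**The concern.** The two documents give different tests and interval levels for the same secondary endpoints, and the SAP does not say why.

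The statistical issue is efficiency. Stratified randomization balances the arms on age and sex. If those factors predict the outcome, the balance reduces the true variability of the treatment difference. An unstratified standard error takes no account of this and comes out too large. The p-value is then too cautious, the interval too wide, and some power is lost. The question is how much, and whether it is the same for Complete Response and mortality.

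**Working it through.** **Inputs from the documents.** 100 patients per arm and a one-sided 0.05 test. SAP 3.2 assumes an IMV "rate of 25% and mortality rate of 12.5% in the placebo group" and a 50% improvement in both on LY3127804. Complete Response failure is therefore taken as 25% vs 12.5%, and mortality as 12.5% vs 6.25%. The plan states no power for either endpoint; its 81% belongs to the primary rank test and is not used here.

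**Assumptions not in the documents.** 40% aged 65 or over, 60% male, permuted blocks of 4, 1, 10 or 20 equal sites, and the prognostic strength of age and sex, which is varied.

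**1. Baseline power, no prognostic effect (Complete Response).** The pooled rate is 0.1875.
- Null SE = √(2 × 0.1875 × 0.8125 / 100) = 0.0552.
- Alternative SE = √((0.25 × 0.75 + 0.125 × 0.875) / 100) = 0.0545.
- Power = Φ((0.125 − 1.645 × 0.0552) / 0.0545) = Φ(0.63) ≈ 73.5%.

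The same formula for mortality (pooled rate 0.09375) gives Φ((0.0625 − 1.645 × 0.0412) / 0.0410) = Φ(−0.13) ≈ 45%.

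**2. Direction, by large-sample formula.** If age and sex explain a share R² of the outcome variance, the actual one-sided error of the unstratified test is 1 − Φ(1.645 / √(1 − R²)).

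| Age OR, sex OR | Complete Response: R², actual error | Mortality: R², actual error |
|---|---|---|
| 1.5, 1.5 | 0.012, 0.049 | 0.007, 0.049 |
| 2, 1.5 | 0.024, 0.048 | 0.014, 0.049 |
| 3, 1.5 | 0.051, 0.046 | 0.029, 0.048 |
| 5, 2 | 0.106, 0.041 | 0.060, 0.045 |

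Example: 1.645 / √(1 − 0.106) = 1.74, and 1 − Φ(1.74) = 0.041. Mortality is less affected because, at a low event rate, the same odds ratios explain less variance.

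**3. Size, by simulation.** 40,000 trials per setting with N = 200. The pooled chi-square z and the four-stratum CMH z are each compared with 1.645. Ranges are over 1, 10 and 20 sites. Monte Carlo SE is about 0.2 points for power and 0.1 for error. Prognostic strength is given here as risk ratios.

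Complete Response:

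| Age RR, male RR | Chi-square error | Power, chi-square | Power, CMH | Points lost | Wald SE too large by | 90% CI coverage |
|---|---|---|---|---|---|---|
| 2, 1.2 | 4.6–4.9% | 74.2–74.4% | 75.0–75.1% | 0.7–0.8 | 0–1% | 90.1–90.4% |
| 3, 1.5 | 4.2–4.3% | 74.6–75.2% | 76.8–77.4% | about 2.2 | 2–4% | 90.7–91.0% |
| 5, 1.5 (extreme) | 3.4–3.8% | 75.1–75.6% | 79.3–79.9% | 4.1–4.3 | 4–8% | 90.9–92.3% |

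The half-width of the 90% interval is 8.9 points (Wald) vs 8.6 (Mantel-Haenszel) in the middle row, and 8.9 vs 8.3 in the last. CMH error is 4.9–5.2%, and Mantel-Haenszel coverage (Sato variance) is 89.6–90.1%. If every planned death occurred without IMV, failure would be 25% + 12.5% = 37.5% vs 18.75%. The losses with 10 sites are then 0.8, 1.8 and 3.0 points.

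Mortality, same risk ratios:

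| Age RR | Points lost | Wald SE ratio | 90% CI coverage |
|---|---|---|---|
| 2 | −0.1 to 0.3 | 0.99–1.00 | 89.6–89.9% |
| 3 | 0.6–1.2 | 1.00–1.01 | 89.9–90.5% |
| 5 | 1.5–2.2 | 1.01–1.03 | 90.2–90.9% |

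**4. Cost of stratifying if age and sex are not prognostic.** CMH loses 0.1–0.4 points (Complete Response) and 0–0.5 (mortality). A repeat with 6,000 trials per setting gave 0.3 to 0.7.

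**5. Why not restore the protocol's site-adjusted model.** Expected deaths are 12.5 + 6.25 = 18.75. With 10 sites of 20 patients, the chance that a given site has no deaths is 0.875¹⁰ × 0.9375¹⁰ = 0.138. The chance that at least one site has none is 1 − (1 − 0.138)¹⁰ = 0.77, and such a site has no finite estimate in a logistic model. In 4,000-trial runs, Wald logistic regression with 10 site terms rejected a true null in 5.3% to 6.6% of trials.

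**The case against.** The strongest reply is that little is at stake. The chi-square test is prespecified and valid after stratified randomization, and it errs toward caution. The 90% level matches the one-sided 0.05 test. Protocol 10.3.1 allows non-principal method changes without an amendment and puts their justification in the clinical study report, so the SAP's silence is not a breach. The primary endpoint, which already combines ventilation and death, is stratified. All of this stands.

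Complete Response is also not the only unstratified analysis, since the log-rank test ignores the strata too. That is true, but no reason is given there either.

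The proposed remedy follows neither document, and the sparse-site argument supports leaving the protocol's model. This is correct as far as site is concerned. It does not justify dropping age and sex, which form only four strata. The 77% figure also ignores the site pooling in SAP 4.5, so it is illustrative.

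SAP 4.16.1 reports the unblinded futility analysis as already done, and SAP 4.6 plans no multiplicity adjustment, so a late change of test invites questions. This is a real cost, and it determines how the change must be made.

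The size rests on assumptions, and the low figure for mortality supposes that age is not far more prognostic for death than for Complete Response. With an age odds ratio of 10 and a sex odds ratio of 2 for death, the loss is about 3 points (45.5% vs 48.9%, one site). Small age-by-sex-by-site strata also weaken the balance: one 4,000-trial run at odds ratios 5 and 2 gave an error of 5.3% for Complete Response, with a simulation SE of about 0.35 points. Finally, N = 200 is the completer target. Up to about 210 patients could be analysed, and imputed non-responders were not modelled.

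**Conclusion.** The concern holds. For Complete Response, the SAP ignores strata that the trial randomizes by and that the protocol's model includes. If age and sex are prognostic, the test is mildly conservative: about 1 to 2 power points are lost at weak to moderate strength, and about 4 in an extreme case. The Wald standard error is up to 4% too large in the first two cases and up to 8% in the extreme one. Type I error is not inflated. For mortality the loss is 0 to about 2 points and the interval is essentially right, so the argument there is consistency.

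The direction follows from the design. The size depends on prognostic strength, age and sex mix, block size and number of sites, none of which the documents give. This is a modest efficiency gain and a needed reconciliation of the two documents; it is not a validity problem.

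**What to change.** In SAP 4.1:

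- For Complete Response, use a CMH test (one-sided 0.05) and a Mantel-Haenszel risk difference with a 90% interval over the four age-group-by-sex strata. Use the same for mortality, for consistency.
- State that site is left out because events are few.
- Keep the unstratified chi-square test and Wald interval as a sensitivity analysis.
- Record in the SAP and the clinical study report that this method and the 90% level replace the protocol's logistic model and 95% interval.

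Staff blinded to treatment and to the interim results should make and date the change before database lock.

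The cost is minor programming and no new data. If age and sex turn out not to be prognostic, up to about 0.7 power points are given up. The change also has to be documented as one made to secondary analyses after an unblinded interim.
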